#### B-2.2.2 Staged enrollment plan procedures

On a daily basis, the site research assistant will review the list of newborns who are hospitalized for routine post-birth care and identify those neonates who are potentially eligible for the study. The research assistant will approach the parent(s) of an eligible hospitalized newborn after discussion with a healthcare provider (e.g. nurse) who is caring for the newborn to ensure that it is a good time to approach the family (e.g., the mother is stable medically, not sleeping, etc). The research assistant will discuss the study with the parent(s) of an eligible newborn and, if the parent(s) is interested in participating, have the parent(s) read and sign the informed consent form.

At the time that the parent signs the informed consent form, a new study file will be opened. Each file has a unique study ID number assigned. The research assistant will record the subject's medical record number next to the assigned study ID number on the **Site Enrollment Log**. The research assistant will also record the date that the informed consent was signed. The signed consent form will be put in the appropriate study file.

After the consent form has been signed, the research assistant will ask the parent(s) to complete the **Parent Enrollment Form**, providing the sex, race and ethnicity of the newborn. The research assistant will also obtain the enrolled subject's date and time of birth from the subject's medical record. The research assistant will complete the **Subject Enrollment Case Report Form**, which includes the subject's sex, race and ethnicity (abstracted from the **Parent Enrollment Form**), and date and time of birth. In addition, the research assistant will confirm on the **Subject Enrollment Case Report Form** that the subject was born at  $\geq 35$  weeks gestation (based on review of the subject's medical record) by checking the appropriate box on the form

At enrollment, the research assistant will explain the timing for the study visit with the parent(s). Prior to hospital discharge, the research assistant will schedule the study visit with the parent(s) for when an enrolled newborn is 2-6 days old. If possible, the study visit will be scheduled at the same time as a clinical visit for the enrolled subject.

#### B-2.3. Procedures for the study visit

Study visits will occur simultaneously with enrollment at sites using the Simultaneous enrollment plan and at a later time for subjects enrolled at sites using the Staged enrollment plan. At the beginning of the study visit at all sites, the research assistant will confirm on the **Study Visit Case Report Form** that the subject does not have any exclusions for participation. Specifically, the research assistant will check the appropriate boxes on the CRF to verify that the subject: 1) is <192 hours old, 2) has not received phototherapy for treatment of hyperbilirubinemia, and 3) that the patient has not been excluded by the site PI. After confirming that the subject is eligible, the research assistant will obtain a series of images using the BiliCam app installed on the iPhone 5s assigned to the study.

Once the research assistant has obtained image data on a study participant using the BiliCam app installed on the iPhone 5s, additional image data (the same series of images) will be obtained using the BiliCam app installed on the iPhone 7 assigned to the study, if possible. At the discretion of the research assistant, these additional images may not be acquired if not practically possible (e.g. the newborn has become too fussy). The procedures for obtaining the images with the iPhone 5s and iPhone 7 are provided in Appendix 2.

#### B- 2.3.1 Procedures for obtaining TSB values for subjects

At sites using the Staged enrollment plan, blood will be obtained by a qualified phlebotomist on study subjects immediately before, or after, the images for the BCB are obtained (i.e. within 2 hours) and sent for assay by the clinical laboratory at each site. At these sites, some study visits will occur at the time of a clinical visit. If the clinicians evaluating the baby at the clinical visit (occurring simultaneously with the study visit) determine that a TSB level is needed for clinical purposes, a second blood sample for the study will not be obtained; the TSB level obtained for clinical purposes will be used as the study value. No blood will be obtained for study purposes at sites using the Simultaneous enrollment plan. At these sites, BiliCam images will be obtained at the time (within 2 hours) of a blood draw for a TSB level that is being obtained for clinical purposes.

#### B -2.3.2. Completing the Study Visit Case Report Form

After obtaining the BCB result on the mobile phone assigned to the study, the research assistant will record the value, and the date and time that the images were obtained, on the **Study Visit Case Report Form**. If a BCB value was not obtained, the research assistant will record "N/A" for the result, and indicate the reason why the BCB value was not available. Possible reasons for not obtaining a BCB value include not obtaining all needed images, issues with lighting, no value downloaded to phone after images are submitted to the server, or a value reported as ">20.0," i.e. outside of measuring range of the device. The initials of the research staff who performed the BiliCam test will be recorded on the CRF.

The calibration card used for the BiliCam test will be affixed to page 2 of the **Study Visit Case Report Form** in the spot indicated on the form.

At the time that the "study" TSB level result is available from the clinical laboratory at each site on a study subject, the level (in mg/dL) will be recorded on the **Study Visit Case Report Form**. In addition, the date and time that the blood was reported as being obtained will also be recorded on the CRF. For subjects in whom the "study" TSB level is a value that was obtained for clinical purposes (including all subjects from Simultaneous enrollment plan sites and a portion of subjects at sites using the Staged enrollment plan), if more than one valid level was obtained within 2 hours of the time that the BiliCam images are obtained, the TSB level drawn closest to the time that the BiliCam images were obtained will be selected as the "study" value. On the **Study Visit Case Report Form** the research assistant will indicate whether the listed TSB value was obtained specifically for the study or for clinical purposes. If no valid TSB level is available, the research assistant will record "N/A" for the result and indicate the reason on the form. Possible reasons include a blood sample that was too hemolyzed for analysis, an inadequate sample (i.e. quantity of blood not sufficient for the assay), and parents declining a study blood draw.

Research staff will document on the **Site Enrollment Log** when the **Study Visit Case Report Form** was completed on each subject by recording the date in the appropriate box on the log for the appropriate Study ID number. If the subject does not have a study visit (i.e. the subject's parent(s) withdraws consent prior to the visit, the subject is excluded by the site principal investigator, the subject is excluded because of phototherapy, the subject is lost to follow-up, or another reason), "N/A" will be recorded in the appropriate box on the **Site**

## Enrollment Log.

### B-2.3.3. Completing the iPhone 7 Case Report Form

In addition to the **Study Visit Case Report Form** on each subject, the research assistant will also note if additional image data were obtained on the study participant using the BiliCam app installed on the iPhone 7 using the **iPhone 7 Image Collection Case Report Form** (appendix 1). If image data were obtained, the research assistant will check the “yes” box on the CRF. If no images with the iPhone 7 were obtained, the research assistant will indicate the reason on the CRF. Possible reasons include, “No, participant too fussy,” “No, parents declined,” or “No, problem with phone/app.” Note that no BCB value will be returned to the iPhone 7 during this study.

### B-2.3.3. Documenting adverse events

Because of the minimal risk nature of the study, it is anticipated that adverse events to subjects related to use of the BiliCam device will be infrequent and, if they occur, mild in severity. If an adverse event occurs for a subject during use of the BiliCam device (study mobile phone, BiliCam app, color calibration card) or during the study blood draw (Staged enrollment plan sites only) it will be documented on the **Adverse Event Case Report Form** (appendix 1). On the CRF, research staff will provide a narrative of the event, the site PI will determine the relationship to the device and this determination will be recorded on the form using the following guidelines:

- **Likely Related:** An adverse event that follows a reasonable temporal sequence from use of BiliCam with the subject, follows a known or expected response pattern to the suspected intervention, that is confirmed by improvement on stopping and reappearance of the event on repeated exposure and that could not be reasonably explained by the known characteristics of the subject’s clinical state.
- **Possibly Related:** An adverse event that follows a reasonable temporal sequence following the use of BiliCam with a subject, but that could readily have been produced by a number of other factors.
- **Not related:** The adverse event is clearly not related to use of BiliCam with a subject. - i.e. another cause of the event is most plausible; and/or a clinically plausible temporal sequence is inconsistent with the onset of the event and the study intervention and/or a causal relationship is considered biologically implausible.

The date of resolution of the adverse event will be noted on the CRF along with a narrative description of the outcome. The severity of the adverse event will also be categorized on the CRF using the following guidelines:

- **Mild:** Awareness of signs or symptoms, but easily tolerated and are of minor irritant type causing no loss of time from normal activities. Symptoms do not require therapy or a medical evaluation; signs and symptoms are transient.
- **Moderate:** Events introduce a low level of inconvenience or concern to the participant and may interfere with daily activities, but are usually improved by simple therapeutic measures; moderate experiences may cause some interference with functioning
- **Severe:** Events interrupt the participant’s normal daily activities and generally require systemic drug therapy or other treatment; they are usually incapacitating

The research staff will also classify each adverse event as serious or not. An adverse event will be classified as serious if it: results in death, is life-threatening, requires hospitalization, results in significant or permanent disability, causes birth defects or may require medical or surgical intervention to prevent one of these outcomes. Completed **Adverse Event Case Report Forms** will be reviewed and signed by the site principal investigator. The study monitor will be notified as soon as possible whenever an Adverse Event Case Report Form is completed. The study monitor will notify the sponsor in any case in which an unanticipated adverse device event occurs.

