## **C. RISK ANALYSIS**

There will be blood draws exclusively for the study at sites using the Staged enrollment plan. There is minor pain from the blood draws. The blood drawing procedure may make some infants and their parents anxious. Both of these risks are transient. A study-specific blood draw is not necessary at the sites using the Simultaneous enrollment plan.

At all sites, there is the risk of loss of privacy from the collection of dates and time of birth, dates and time of blood collection for TSB levels that are ordered clinically, and race and ethnicity information collected for the study. There is also a risk loss of privacy of infants on whom image data are obtained and stored on the study computer server. However, the images will not include identifying information (i.e. the images do not include faces).

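### Adverse events from the study blood draw are collected but rated only for relatedness to the device, and a serious one has no stated prompt route to the sponsor

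*Combined protocol and SAP*

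**What the plan says.** Section B-2.3.3 (Documenting adverse events) defines two exposures for adverse event collection. One is use of the device: phone, app and calibration card. The other is the research blood sample: an event "during the study blood draw (Staged enrollment plan sites only) it will be documented" on the Adverse Event CRF.

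For causality, "the site PI will determine the relationship to the device and this determination will be recorded on the form". Three categories follow, each anchored to BiliCam. Not related reads: "The adverse event is clearly not related to use of BiliCam with a subject", explained by, among other things, the condition that "another cause of the event is most plausible". Possibly Related needs a reasonable time sequence after BiliCam use, "but that could readily have been produced by a number of other factors".

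The same section has staff record a narrative, outcome, resolution date and severity, and classify each event as serious or not. The site principal investigator signs the form, and the study monitor is told promptly of every completed form. The next step is narrower: "The study monitor will notify the sponsor in any case in which an unanticipated adverse device event occurs".

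Section B-2.6 adds that copies of completed Adverse Event CRFs are checked for PHI, collated and passed to the sponsor. Section C (Risk Analysis) confirms that the draw is a research procedure: "There will be blood draws exclusively for the study at sites using the Staged enrollment plan".

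**The concern.** The plan brings the blood draw into safety collection but then asks a causality question that does not cover it. The omission does not look like a decision on scope, because draw events are included explicitly in the same paragraph.

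The draw is the study's only invasive procedure. Apart from loss of privacy, pain and anxiety from it are the only risks that Section C names. Under B-2.3.1, no second sample is taken when clinicians order a TSB at the visit, so study-only draws fall on newborns whose clinicians did not ask for one. For these infants, a structured record of harm from the research procedure, and a defined path for a serious event, are what one would expect. Without them, anyone tabulating events by relatedness could not separate draw-related events from truly incidental ones, and a serious draw event could wait for a transfer with no stated date.

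**Working it through.** No power or error-rate calculation is involved. The check traces an injury caused by the study blood draw through the reporting rules, then works out how many newborns could be exposed.

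**Trace of a draw-caused event**

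1. *Recorded on the Adverse Event CRF?* Yes (B-2.3.3).
2. *Relatedness to the draw rated?* No such rating is described. The only one described is to the device.
3. *Which device rating results?* Not related fits best, because the draw is a more plausible cause than the camera or card. The text does not force it. B-2.3.1 places the draw immediately before or after imaging, within 2 hours, so where the draw follows imaging Possibly Related is also open. The first rating is correct about the device but silent about the draw. The second charges the device with an event it did not cause.
4. *Severity and seriousness recorded?* Yes, but no reporting step in the section depends on the seriousness classification.
5. *Study monitor told?* Yes, promptly, for every completed form.
6. *Event-triggered notice to the sponsor?* Not required by the text, even for a serious event. The sole trigger is an unanticipated adverse device event. The section does not define that term; on its ordinary meaning it does not cover a puncture injury.
7. *Does the sponsor receive the form?* Yes, as a collated copy under B-2.6, with no filter on relatedness and no stated timing.

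Steps 2 and 6 are separate gaps. The notification trigger is not keyed to the relatedness rating, so correcting one does not correct the other.

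**Newborns exposed**

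Inputs: overall cap of 375 enrolled; at most 150 enrolled at a Staged site and 75 at a Simultaneous site (C-2.0); 225 completers, 75 at each site (B-2.7.1); at least 3 sites (B-2.0).

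- The completer target implies 225 / 75 = 3 sites. With *s* Staged sites, 150*s* + 75(3 − *s*) = 375 gives 75*s* = 150, so *s* = 2. Completers at Staged sites: 2 × 75 = 150.
- With four sites, which the minimum of 3 allows, 150*s* + 75(4 − *s*) = 375 gives 75*s* = 75, so *s* = 1 and 1 × 75 = 75.

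The three-site reading fits B-2.7.1 better. On these two readings the exposed group is up to about 75 to 150 completers, less those whose TSB was drawn for clinical purposes. The documents give no figure for that deduction. These are counts of draws, not of expected injuries.

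**The case against.** The strongest reply is that the system already captures these events. Every completed form reaches the monitor promptly, whatever the rating. Under Section E that monitor represents a CRO chosen by the sponsor to oversee the trial, and monitoring visits include checking adverse event reporting and discussing emerging problems. The narrative would describe a draw injury as such, and Not related is a truthful answer to a question about the device. Two of the three definitions also mention an intervention in more general words. The expected harm is small: Section C calls the pain minor and both risks transient, and C-1.0 limits the sample to 1 mL drawn by an experienced phlebotomist.

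Much of this stands, and it rules out several stronger readings that a reader might infer:

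- *That the sponsor would never learn of a draw injury.* B-2.6 sends it copies of the completed forms.
- *That every draw event would be coded Not related.* Possibly Related remains available.
- *That the safety record would show no study-caused harm.* Narrative, outcome and seriousness are all recorded.
- *That a cluster at one Staged site would go unseen.* The monitor hears of each event.

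What the reply does not supply is a structured attribution to the draw, or a stated duty on the monitor to pass a serious draw event to the sponsor promptly. The general wording inside the definitions does not change the question that the site principal investigator is asked, which concerns the device.

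**Conclusion.** The point holds as a gap in safety attribution and prompt reporting. Followed as written, an injury from a study-only draw gets no relatedness rating to the procedure that caused it, and a serious one has no event-triggered route from monitor to sponsor. It does not disappear from the record.

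The group concerned is up to about 150 completers if two of three sites are Staged, or about 75 if there is one Staged site among four, in each case less those with a clinical TSB. The site mix is inferred from the caps. Few events are expected, and neither the correlation endpoint nor its acceptance criterion is affected.

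The conclusion rests on two assumptions: that the Adverse Event CRF in Appendix 1, which was not available for review, has no field for relatedness to the procedure; and that unanticipated adverse device event carries its ordinary meaning. If the form already has that field, the first gap reduces to protocol wording and the notification gap remains. This is a cheap improvement worth making, not a flaw that threatens the study.

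**What to change.** Two changes to B-2.3.3 (Documenting adverse events):

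1. Have the site principal investigator record two determinations with the same categories: relationship to the BiliCam device and, separately, relationship to the study blood draw, with N/A where no study draw was done. Reword the category definitions so that each can be read for either exposure. Add the matching field to the Adverse Event CRF if it is not there already.
2. Extend the sponsor-notification sentence so that, besides unanticipated adverse device events, the monitor promptly notifies the sponsor of any serious adverse event related to the device or to the study blood draw.

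The cost is one form field, a few lines of protocol text and slightly more reporting work. Eligibility, study procedures, sample size and analysis are unchanged.

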#### B-2.3.4. Modifying the app

No modifications to the app impacting clinical function are anticipated during the study. If modifications of the app are made during the study, all site investigators will be notified and the changes will be evaluated and accounted for in the analysis of study data.

#### B-2.4. Procedures for use of additional study forms

**Site Principal Investigator Exclusion Explanation Form**— The site principal investigator may exclude enrolled subjects from completion of the study for medical, or other reasons. Examples include: a subject develops medical complications after enrollment that precludes study completion, or Child Protection/Child Welfare Services assume custody of a subject prior to study completion. If the site principal investigator determines that a subject should be excluded from the study after enrollment, this form will be completed to briefly explain the decision. (Copy of form included in appendix 1).

**BiliCam Incident Report Form**-- This form will be completed whenever there is an issue with the BiliCam app installed on a mobile phone assigned to the study. Listed issues include: app closing (“crashing”) while preparing to obtain images, while obtaining images or while trying to submit images; inability to submit images; problems with “auto capture” of images, failure in receiving BCB level, issues with lighting, and others. The form will be completed by the research staff individual who experienced the issue and will also include comments. Note: This form will not be included in the study file for individual subjects, but completed on an ad hoc basis. (Copy of form included in appendix 1). Completed forms will be sent to the study monitor.

**Protocol Deviation and Other Problems Report Form**—This form should be completed when there is a deviation from the approved protocol; examples might include consenting issues, inadvertently enrolling ineligible participants, or collecting data on a participant outside of the approved age. Other problems might include: losing study phones or having them stolen, inadvertent disclosure of study data or losing study data.

When completing the form, no identifying information about a participant should be included. The research assistant or site principal investigator should record the date when the form was completed and the site. If the event involves one specific participant, the participant’s study ID should be listed on the form. If multiple participants are involved, record “N/A” for participant study ID and list the study ID numbers in the narrative section of the form. If no specific participant was involved in the event, record “N/A” for study ID.

The form consists of three narrative sections. For the first part, a description of the actual protocol deviation or other issue should be provided. In the second part of the report form, the factors that led to the event occurring (i.e. why the protocol deviation or other issue happened) should be described. In the final narrative section, actions taken to ensure that the event will not recur should be described.

When a protocol deviation or other issue occurs, it should be noted on the form whether the problem affected any subject’s rights, safety or well-being and/or if the scientific integrity of the investigation was affected. If the answer to this item on the form is “yes,” the site IRB should be notified.

Once the form has been completed, it should be signed and dated by the site principal investigator. The study monitor should be notified as soon as possible if a protocol deviation or other problem that warrants completion of the **Protocol Deviation and Other Issues Report Form** occurs. The completed form will be provided to the study monitor. In addition, as needed, the site IRB should be notified about the event.

**“Note to file” form--** An additional form will be included in the study file for each subject that is to be completed as needed when unusual events or problems occur. This form will also be used to provide explanations when a subject does not complete the study, unless the explanation is provided elsewhere (e.g. in the **Site Principal Investigator Exclusion Explanation Form**). (Copy of form included in appendix 1).

